### **13.3 Publication of study protocol and results**

The protocol will be registered in a publicly accessible database such as [clinicaltrials.gov](http://clinicaltrials.gov) and as required in EudraCT. In addition, after study completion (defined as last patient last visit) and finalization of the study report the results of this trial will be submitted for publication and posted in a publicly accessible database of clinical trial results, such as the Novartis clinical trial results website and all required Health Authority websites (e.g. [Clinicaltrials.gov](http://Clinicaltrials.gov), [EudraCT](http://EudraCT) etc.)

For details on the Novartis publication policy including authorship criteria, please refer to the Novartis publication policy training materials that were provided to you at the trial investigator meetings.

### **13.4 Quality Control and Quality Assurance**

Novartis maintains a robust Quality Management System (QMS) that includes all activities involved in quality assurance and quality control, to ensure compliance with written Standard Operating Procedures as well as applicable global/local GCP regulations and ICH Guidelines.

Audits of investigator sites, vendors, and Novartis systems are performed by auditors, independent from those involved in conducting, monitoring or performing quality control of the clinical trial. The clinical audit process uses a knowledge/risk based approach.

Audits are conducted to assess GCP compliance with global and local regulatory requirements, protocols and internal SOPs, and are performed according to written Novartis processes.

## **14 Protocol adherence**

This protocol defines the study objectives, the study procedures and the data to be collected on study participants. Additional assessments required to ensure safety of participants should be administered as deemed necessary on a case by case basis. Under no circumstances including incidental collection is an investigator allowed to collect additional data or conduct any additional procedures for any purpose involving any investigational drugs under the protocol, other than the purpose of the study. If despite this interdiction prohibition, data, information, observation would be incidentally collected, the investigator shall immediately disclose it to Novartis and not use it for any purpose other than the study, except for the appropriate monitoring on study participants.

Investigators ascertain they will apply due diligence to avoid protocol deviations. If an investigator feels a protocol deviation would improve the conduct of the study this must be considered a protocol amendment, and unless such an amendment is agreed upon by Novartis and approved by the IRB/IEC and Health Authorities, where required, it cannot be implemented.

#### **14.1 Protocol amendments**

Any change or addition to the protocol can only be made in a written protocol amendment that must be approved by Novartis, health authorities where required, and the IRB/IEC prior to implementation.

Only amendments that are required for participant safety may be implemented immediately provided the health authorities are subsequently notified by protocol amendment and the reviewing IRB/IEC is notified.

Notwithstanding the need for approval of formal protocol amendments, the investigator is expected to take any immediate action required for the safety of any participant included in this study, even if this action represents a deviation from the protocol. In such cases, Novartis should be notified of this action and the IRB/IEC at the study site should be informed according to local regulations.

## 16 Appendices

### 16.1 Appendix 1: Clinically notable laboratory values and vital signs

Vital signs range deviations are defined in [Table 16-1](#):

**Table 16-1 Clinically notable vital signs**

Vital sign		Notable abnormalities
Pulse (beats/min)		either $\geq 120$ + increase $\geq 25^*$ or $> 130$ either $\leq 50$ + decrease $\geq 30^*$ or $< 40$
BP (mmHg)	systolic	either $\geq 180$ + increase $\geq 30^*$ or $> 200$ either $\leq 90$ + decrease $\geq 30^*$ or $< 75$
	diastolic	either $\geq 105$ + increase $\geq 20^*$ or $> 115$ either $\leq 50$ + decrease $\geq 20^*$ or $< 40$

\* Refers to post-BL value as compared to BL value

Notable laboratory values are defined in [Table 16-2](#):

**Table 16-2 Clinically notable laboratory abnormalities for selected tests**

Parameters	Criteria
Hematology	
Hemoglobin	$\leq 10$ g/dL
Hematocrit	$\leq 0.8 \times \text{LLN}$
WBC (total)	$\leq 2.8 \times 10^3 / \mu\text{L}$ , $\geq 16 \times 10^3 / \mu\text{L}$
Platelet count	$\leq 75 \times 10^3 / \mu\text{L}$ , $\geq 700 \times 10^3 / \mu\text{L}$
Clinical chemistry	
Creatinine	$> 2$ mg/dL
CPK	$> 1$ and $\leq 3 \times \text{ULN}$
CPK	$> 3$ and $\leq 5 \times \text{ULN}$
CPK	$> 5$ and $\leq 10 \times \text{ULN}$
CPK	$> 10 \times \text{ULN}$
ALT	$> 1$ and $\leq 3 \times \text{ULN}$
ALT	$> 3$ and $\leq 5 \times \text{ULN}$
ALT	$> 5 \times \text{ULN}$
AST	$> 1$ and $\leq 3 \times \text{ULN}$
AST	$> 3$ and $\leq 5 \times \text{ULN}$
AST	$> 5 \times \text{ULN}$
Total bilirubin	$> 2 \times \text{ULN}$
ALP	$> 2 \times \text{ULN}$

## 16.2 Appendix 2: Liver event and laboratory trigger definitions & follow-up requirements

**Table 16-3 Liver event and laboratory trigger definitions**

	Definition/ threshold
Liver laboratory triggers If ALT, AST and total bilirubin normal at baseline:	
 
• ALT or AST > 5 × ULN
 
• ALP > 2 × ULN (in the absence of known bone pathology)
 
• Total bilirubin > 3 × ULN (in the absence of known Gilbert syndrome)
 
• ALT or AST > 3 × ULN and INR > 1.5
 
• Potential Hy's Law cases (defined as ALT or AST > 3 × ULN and Total bilirubin > 2 × ULN [mainly conjugated fraction] without notable increase in ALP to > 2 × ULN)
 
• Any clinical event of jaundice (or equivalent term)
 
• ALT or AST > 3 × ULN accompanied by (general) malaise, fatigue, abdominal pain, nausea, or vomiting, or rash with eosinophilia
 
• Any adverse event potentially indicative of a liver toxicity*
 

If ALT or AST abnormal at baseline:	
 
• ALT or AST > 2x baseline or > 300 U/L (whichever occurs first)
 

\*These events cover the following: hepatic failure, fibrosis and cirrhosis, and other liver damage-related conditions; non-infectious hepatitis; benign, malignant and unspecified liver neoplasms ULN: upper limit of normal

**Table 16-4 Follow up requirements for liver laboratory triggers with liver symptoms**

ALT or AST	TBL	Liver Symptoms	Action
ALT or AST increase without bilirubin increase:			
If normal at baseline: ALT or AST > 3 x ULN  If elevated at baseline: ALT or AST > 2 x baseline or > 300 U/L (whichever occurs first)	Normal For patients with Gilbert's syndrome: No change in baseline TBL	None	
 
• No change to study treatment
 
• Measure ALT, AST, ALP, GGT, TBL, direct and indirect bilirubin, PT/INR, albumin, CPK, and GLDH in 48-72 hours.
 
• Follow-up for symptoms.
 

ALT or AST	TBL	Liver Symptoms	Action
If normal at baseline: ALT or AST > 5 x ULN for more than two weeks  If elevated at baseline: ALT or AST > 3 x baseline or > 300 U/L (whichever occurs first) for more than two weeks	Normal  For patients with Gilbert's syndrome: No change in baseline TBL	None	
 
• Interrupt study drug
 
1. Measure ALT, AST, ALP, GGT, TBL, direct and indirect bilirubin, PT/INR, albumin, CPK, and GLDH in 48-72 hours.
 
• Follow-up for symptoms.
 
• Initiate close monitoring and workup for competing etiologies.
 
• Study drug can be restarted only if another etiology is identified and liver enzymes return to baseline.
 

If normal at baseline: ALT or AST > 8 x ULN	Normal	None	
ALT or AST increase with bilirubin increase:			
If normal at baseline: ALT or AST > 3 x ULN  If elevated at baseline: ALT or AST > 2 x baseline or > 300 U/L (whichever occurs first)	TBL > 2 x ULN (or INR > 1.5)  For patients with Gilbert's syndrome: Doubling of direct bilirubin	None	
If normal at baseline: ALT or AST > 3 x ULN  If elevated at baseline: ALT or AST > 2 x baseline or > 300 U/L (whichever occurs first)	Normal or elevated	Severe fatigue, nausea, vomiting, right upper quadrant pain	

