#### **6.5.1 Dose modifications**

Study drug administration of inclisiran [inclisiran (KJX839), 284 mg liquid in PFS, 1.5 ml] should be temporarily interrupted or permanently discontinued in participants with:

1. Intolerable AEs, or if the investigator believes that continuing dosing will be detrimental to the participant's mental or physical health. This includes severe or serious reactions at the injection site and any anaphylactic type reactions.
2. Liver laboratory values meeting the study drug interruption criteria listed in Table 16-4 and Table 16-5.
3. Unexplained creatine phosphokinase (CPK) values  $>5 \times$  ULN confirmed by repeat test when the CPK elevation is associated with muscle pain, muscle tenderness and/or muscle weakness, or new onset renal dysfunction.

Study treatment may be restarted at the discretion of the investigator, if the reason for discontinuation has resolved.

The dose interruptions must be recorded on an appropriate eCRF.

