**Table 16-5 Follow up requirements for liver laboratory triggers**

Criteria	Actions required	Follow-up monitoring
Total Bilirubin (isolated)		
>1.5 – 3.0 ULN	
 
• Maintain treatment
 
• Repeat LFTs within 48-72 hours
 
	Monitor LFTs weekly until resolution a to ≤ Grade 1 or to baseline
> 3 - 10 × ULN (in the absence of known Gilbert syndrome)	
 
• Interrupt treatment
 
• Repeat LFT within 48-72 hours
 
	Monitor LFTs weekly until resolution a to ≤ Grade 1 or to baseline (ALT, AST, total

Criteria	Actions required	Follow-up monitoring
	
 
• Hospitalize if clinically appropriate
 
• Establish causality
 
• Record the AE and contributing factors (e.g. conmeds, med hx, lab) in the appropriate eCRF
 
	bilirubin, Alb, PT/INR, ALP and GGT) Test for hemolysis (e.g. reticulocytes, haptoglobin, unconjugated [indirect] bilirubin)
> 10 x ULN	
 
• Discontinue the study treatment immediately
 
• Hospitalize the participant
 
• Establish causality
 
• Record the AE and contributing factors(e.g. conmeds, med hx, lab) in the appropriate eCRF
 
	ALT, AST, total bilirubin, Alb, PT/INR, ALP and GGT until resolution c (frequency at investigator discretion)
Any AE potentially indicative of a liver toxicity*	
 
• Consider study treatment interruption or discontinuation
 
• Hospitalization if clinically appropriate
 
• Establish causality
 
• Record the AE and contributing factors(e.g., conmeds, med hx, lab) in the appropriate eCRF
 
	Investigator discretion

aResolution is defined as an outcome of one of the following: (1) return to baseline values, (2) stable values at three subsequent monitoring visits at least 2 weeks apart, (3) remain at elevated level after a maximum of 6 months, (4) liver transplantation, and (5) death.

Based on investigator's discretion investigation(s) for contributing factors for the liver event can include: Serology tests, imaging and pathology assessments, hepatologist's consultancy; obtaining more detailed history of symptoms and prior or concurrent diseases, history of concomitant drug use, exclusion of underlying liver disease.

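### Table 16-4 drops its transaminase hold in asymptomatic participants when bilirubin is above 1 and up to 2 x ULN with INR at or below 1.5

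*Protocol*

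**What the plan says.** Among the reasons to interrupt or stop inclisiran, Protocol Section 6.5.1 lists "Liver laboratory values meeting the study drug interruption criteria listed in Table 16-4 and Table 16-5". Table 16-4 (Appendix 2, Section 16.2) has five rows in two blocks.

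The first block is headed "ALT or AST increase without bilirubin increase". All three of its rows require normal total bilirubin (TBL) and no symptoms:

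- Row 1: ALT or AST > 3 x ULN (raised baseline: > 2 x baseline or > 300 U/L). Study treatment is unchanged and a liver panel is repeated in 48-72 hours.
- Row 2: "ALT or AST > 5 x ULN for more than two weeks" (raised baseline: > 3 x baseline or > 300 U/L, also for more than two weeks). Study drug is interrupted.
- Row 3: "ALT or AST > 8 x ULN", for a normal baseline only. Study drug is interrupted.

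The second block covers a transaminase rise with a bilirubin rise:

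- Row 4: the row 1 transaminase thresholds, no symptoms, and "TBL > 2 x ULN (or INR > 1.5". Study drug is interrupted.
- Row 5: the same thresholds with listed liver symptoms, at any bilirubin. Study drug is interrupted.

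The action cells of rows 3 to 5 are blank in the text available to us. We read them as one merged cell continuing the interruption printed in row 2.

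The bilirubin rows of Table 16-5 stand under "Total Bilirubin (isolated". Between 1.5 and 3.0 x ULN that table keeps treatment going and repeats the liver tests within 48-72 hours.

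**The concern.** A stopping rule for liver injury should not loosen as bilirubin rises. Here it does: the same transaminase value is held at normal bilirubin, is not held by any row at slightly raised bilirubin, and is held again above 2 x ULN. The documents give no reason for this. Row 5 shows that the table can span all bilirubin levels where that is intended.

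Participant safety is at stake. Section 4.5 relies on stopping rules to limit risk, and Section 6.5.2.1 opens by treating combined transaminase and bilirubin rises as a possible sign of severe drug-induced liver injury. In the gap, a prescribed hold becomes the investigator's judgement.

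**Working it through.** There is no sample-size or power figure to reproduce. The check applies the Table 16-4 rows to a grid of cases.

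**Inputs.** The thresholds are those of rows 1 to 5. The cases are asymptomatic, without Gilbert's syndrome, with INR 1.2. Where row 1 and an interruption row both match, the interruption is taken.

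**Conditions that matter for these cases.** Rows 1-3 need TBL <= 1 x ULN. Row 4 needs TBL > 2 x ULN, because INR 1.2 does not meet its alternative. Row 5 needs symptoms. So 1 < TBL <= 2 x ULN satisfies none of them.

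| Transaminase state | TBL 0.8 | TBL 1.8 | TBL 2.2 |
|---|---|---|---|
| Normal baseline, ALT 4 x ULN | repeat panel | no row | interrupt |
| Normal baseline, ALT 6 x ULN, 1 week | repeat panel | no row | interrupt |
| Normal baseline, ALT 6 x ULN, 3 weeks | interrupt | no row | interrupt |
| Normal baseline, ALT 9 x ULN | interrupt | no row | interrupt |
| Raised baseline, 2.5 x baseline, 1 week | repeat panel | no row | interrupt |
| Raised baseline, 3.5 x baseline, 3 weeks | interrupt | no row | interrupt |

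Six of the 18 cells match no row, all at TBL 1.8. In three of the six states a prescribed interruption lapses. In the other three only the fixed 48-72 hour repeat lapses.

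**Edges of the gap.** For ALT 9 x ULN, a finer grid gives interruption at TBL 0.8 and 1.0, no row at 1.1, 1.5, 1.9 and 2.0, and interruption at 2.1 x ULN. With INR 1.6, or with the listed symptoms, all six states at TBL 1.8 are interrupted.

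**Does other text restore the hold?**

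- Table 16-5: its bilirubin rows are for isolated elevations. Its row for liver-related adverse events only asks that interruption be considered.
- Table 16-3 with Section 10.2.1: at TBL 1.8, with bilirubin normal at baseline in the normal-baseline states, five of the six states are triggers (all but ALT 4 x ULN). That brings repeat tests including INR and, if confirmed, close observation. Interruption is only to be considered.
- For ALT 4 x ULN, Table 16-2 with Section 8.4.1 leaves follow-up tests to the investigator.
- Section 6.5.1 item 1 and Section 9.1.1 allow or require stopping, but only once the investigator judges that there is a risk.

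**Which doses are exposed?** Table 8-1 schedules coagulation tests, and so INR, only at screening, Day 0 and Day 330. At Days 90, 180 and 270 the INR route needs an unscheduled test. Doses fall on Days 0, 90 and 270. If central-laboratory results are not back before a same-day injection (an assumption), scheduled post-baseline results can hold one of the three doses, that of Day 270.

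**Does the restart wording matter?** Table 16-4 says "Study drug can be restarted only if another etiology is identified and liver enzymes return to baseline", while Section 6.5.1 says "Study treatment may be restarted at the discretion of the investigator, if the reason for discontinuation has resolved". Take a last result before Day 270 of ALT 9 x ULN without symptoms. Enzymes are still raised, so neither restart condition is met. The dose is held at TBL 0.8 or 2.2 x ULN under either text, and no row holds it at 1.8 with INR <= 1.5.

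**The case against.** The strongest reply concerns weight. Section 6.5.2.1 goes on to set its own cut-off for combined injury at bilirubin above 2 x ULN. The Hy's Law definitions and the notable-bilirubin limit in Table 16-2 use the same cut-off. A site could take the first block's heading to mean bilirubin not above 2 x ULN, and so apply rows 2 and 3 at 1.8. That reading is sensible, but it conflicts with the word *Normal* in the bilirubin cells of those rows, and a stopping rule should not depend on it.

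Other points stand as limits:

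- Section 6.5.1 says study drug *should* be interrupted, so *prescribed* here means an action the table orders without further judgement. The firmer *must* is in Section 9.1.1.
- If Table 16-5's 1.5 to 3.0 x ULN row were applied despite its heading, its 48-72 hour repeat would apply too, alongside its instruction to maintain treatment. It would still give no hold.
- Six of 18 follows from testing three bilirubin values with one inside the gap. It maps the gap and says nothing about how often a participant falls in it.
- Only the inclisiran arm (about 222 participants) receives study drug, and the combination of values is narrow.
- The merged-cell reading is an inference. The gap does not depend on it, because row 2 prints the interruption and still requires normal bilirubin.

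One point cuts the other way. Exclusion 16 bars bilirubin only above 2 x ULN, so a participant can enter already in the band. With normal ALT and AST at baseline, that participant fits neither baseline heading of Table 16-3, so the Section 10.2.1 fallback is not clearly triggered.

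**Conclusion.** The concern holds and should be corrected. In asymptomatic participants without Gilbert's syndrome, with TBL above 1 and up to 2 x ULN and INR at or below 1.5, Table 16-4 orders no hold for ALT or AST above 8 x ULN, or above 5 x ULN for more than two weeks. The same applies to the raised-baseline equivalent of the two-week criterion. Each of these is held at lower and at higher bilirubin.

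What lapses is the rule, not the ability to hold. A later result showing TBL above 2 x ULN, INR above 1.5, symptoms, or normal TBL with transaminases still over the threshold brings the hold back. No frequency can be derived from the documents. It is expected to be low, and no estimate is made. The conclusion rests on the literal row conditions and, for the above-8 x ULN row and the second block, on the merged-cell reading.

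**What to change.** By written amendment with IRB approval (Section 14.1), change Table 16-4 as follows:

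1. In rows 2 and 3 only, replace the normal-bilirubin condition with TBL <= 2 x ULN. In both, word the Gilbert's exception to cover any change short of a doubling of direct bilirubin, which is where row 4 takes over. Row 3 has no Gilbert's wording now.
2. Amend the first block's heading to match.
3. Leave row 1 limited to normal bilirubin, so that its unchanged-treatment instruction does not spread to raised bilirubin.
4. Optionally, add a row for other ALT or AST values > 3 x ULN (or the raised-baseline equivalent) with TBL above 1 and up to 2 x ULN and INR <= 1.5 or not yet known: repeat the 48-72 hour panel including INR and decide on dosing from that result. This row should also state what to do if the repeat stays in the band.

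Items 1 to 3 restore all three lapsed holds. On the grid, the unmatched cells fall from 6 to 3 of 18. Item 4 brings them to 0. The 12 cells at TBL 0.8 and 2.2 x ULN do not change.

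The cost is two table cells, one heading and, if wanted, one row, plus a few more held doses and unscheduled repeat tests. No scheduled blood draw is added, because ALT, AST and TBL are already measured at every visit.

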**Table 16-5 Follow up requirements for liver laboratory triggers**

Criteria	Actions required	Follow-up monitoring
Total Bilirubin (isolated)		
>1.5 – 3.0 ULN	
 
• Maintain treatment
 
• Repeat LFTs within 48-72 hours
 
	Monitor LFTs weekly until resolution a to ≤ Grade 1 or to baseline
> 3 - 10 × ULN (in the absence of known Gilbert syndrome)	
 
• Interrupt treatment
 
• Repeat LFT within 48-72 hours
 
	Monitor LFTs weekly until resolution a to ≤ Grade 1 or to baseline (ALT, AST, total

Criteria	Actions required	Follow-up monitoring
	
 
• Hospitalize if clinically appropriate
 
• Establish causality
 
• Record the AE and contributing factors (e.g. conmeds, med hx, lab) in the appropriate eCRF
 
	bilirubin, Alb, PT/INR, ALP and GGT) Test for hemolysis (e.g. reticulocytes, haptoglobin, unconjugated [indirect] bilirubin)
> 10 x ULN	
 
• Discontinue the study treatment immediately
 
• Hospitalize the participant
 
• Establish causality
 
• Record the AE and contributing factors(e.g. conmeds, med hx, lab) in the appropriate eCRF
 
	ALT, AST, total bilirubin, Alb, PT/INR, ALP and GGT until resolution c (frequency at investigator discretion)
Any AE potentially indicative of a liver toxicity*	
 
• Consider study treatment interruption or discontinuation
 
• Hospitalization if clinically appropriate
 
• Establish causality
 
• Record the AE and contributing factors(e.g., conmeds, med hx, lab) in the appropriate eCRF
 
	Investigator discretion

aResolution is defined as an outcome of one of the following: (1) return to baseline values, (2) stable values at three subsequent monitoring visits at least 2 weeks apart, (3) remain at elevated level after a maximum of 6 months, (4) liver transplantation, and (5) death.

Based on investigator's discretion investigation(s) for contributing factors for the liver event can include: Serology tests, imaging and pathology assessments, hepatologist's consultancy; obtaining more detailed history of symptoms and prior or concurrent diseases, history of concomitant drug use, exclusion of underlying liver disease.

### 16.3 Appendix 3: Specific Renal Alert Criteria and Actions and Event Follow-up

**Table 16-6 Specific Renal Alert Criteria and Actions**

Renal event	Actions
Confirmed serum creatinine increase (sCR) 25 – 49%	Consider causes and possible interventions Follow up within 2-5 days
Serum creatinine increase $\geq 50\%$ + + OR if <18 years old, eGFR <math>\leq 35</math> mL/min/1.73 m^2 +	Consider causes and possible interventions Repeat assessment within 24-48h if possible Consider drug interruption or discontinuation unless other causes are diagnosed and corrected Consider participant hospitalization and specialized treatment
New onset dipstick proteinuria $\geq 3+$ OR Protein-creatinine ratio (PCR) $\geq 1$ g/g Cr (or mg/mmol equivalent as converted by the measuring laboratory)	Consider causes and possible interventions Assess serum albumin & serum total protein Repeat assessment to confirm Consider drug interruption or discontinuation unless other causes are diagnosed and corrected
New onset hematuria $\geq 3+$ on urine dipstick	Repeat assessment to confirm Distinguish hemoglobinuria from hematuria Urine sediment microscopy Assess sCr Exclude infection, trauma, bleeding from the distal urinary tract/bladder, menstruation Consider bleeding disorder

+ Corresponds to KDIGO (Kidney Disease: Improving Global Outcomes) criteria for Acute Kidney Injury

Additional specialized assessments are available to assess renal function or renal pathology. (Note: In exceptional cases, when a nephrologist considers a renal biopsy, it is recommended to make slide specimen available for evaluation by the RSG to potentially identify project-wide patterns of nephrotoxicity.)

Whenever a renal event is identified, a detailed patient history and examination are indicated to identify and potentially eliminate risk factors that may have initiated or contributed to the event:

- Blood pressure assessment (after 5-minute rest, with an appropriate cuff size)
- Signs and symptoms like fever, headache, shortness of breath, back or abdominal pain, dysuria or hematuria, dependent or periorbital edema
- Changes in blood pressure, body weight, fluid intake, voiding pattern, or urine output
- Concomitant events or procedures such as trauma, surgical procedures, cardiac or hepatic failure, contrast media or other known nephrotoxin administration, or other diseases or causes, e.g., dehydration due to delirium, tumor lysis

